#### 1.2.1.2.2 Clinical efficacy

Based on available data as of 15-Mar-2016, from study [INC280X2102] preliminary clinical activity has been observed with INC280 as single agent therapy in NSCLC. Confirmed partial responses were observed in 11/55 (ORR 20%) evaluable NSCLC patients (defined as those with at least one post-baseline tumor assessment or have discontinued treatment at the time of the data cut-off) enrolled in the 2 expansion phases (treated at the RP2D of 400 mg BID tablet or 600 mg BID capsule) and DCR was 51%. In evaluable patients with cMET IHC 3+ (regardless of GCN), confirmed partial responses were seen in 9/37 patients (ORR 24%) and DCR was 60%, while in evaluable patients with cMET GCN  $\geq$ 6 (IHC 3+, except 2 patients with IHC 2+), confirmed partial responses were seen in 7/15 patients (ORR 47%) and DCR was 80%. Kaplan-Meier median PFS was 3.55 months (95% CI 1.84–7.33) in the total NSCLC population (n=55), while in patients with cMET GCN  $\geq$ 6 median PFS was extended to 7.39 months (95% CI 3.84–22.11). Four NSCLC patients with cMET exon 14 mutations were identified by retrospective NGS analysis: all 4 were IHC3+ and 3/4 had a GCN  $\geq$ 10, while the GCN was missing in 1 patient; confirmed PR was achieved in 3 patients (2 with GCN >10 and 1 with unknown GCN), while one achieved unconfirmed PR (Schuler et al 2016). ALK status was available for 51/55 patients and all 51 (100%) were negative for ALK rearrangement. EGFR status was available in 50/55 patients and 49 (98%) were EGFR wt.

Thus, the preliminary efficacy data suggest that patients with NSCLC whose tumors are EGFR wt and have cMET amplification and/or mutations may obtain therapeutic benefit from treatment with single-agent INC280. Based on these preliminary but promising results, a more

thorough investigation of the activity of INC280 in patients with EGFR wt NSCLC with varying degrees of cMET amplification and/or cMET mutations is warranted in order to determine those individuals most likely to benefit from treatment with single-agent INC280.

Promising activity in cMET mutated NSCLC patients with INC280 as single agent therapy with INC280 400 mg BID, both in pretreated (Cohort 4) and particularly in treatment naïve (Sub-cohort 5b) setting was observed as of 09 Aug 2018 cut-off date: ORR by BIRC was 39.1% (95% CI 27.6–51.6) in 2/3 line patients (n=69, Cohorts 4) and 72.0% (95% CI 50.6–87.9) in treatment naïve patients (n=25, Sub-cohort 5b) (Wolf et al 2018).

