### 10.4.2 Statistical hypothesis, model, and method of analysis

The primary analysis will be performed on the FAS. The primary efficacy endpoint ORR will be estimated and the exact 95% confidence interval (CI) ([Clopper and Pearson 1934](#)) provided by cohort/sub-cohort.

In Cohorts 1-4, treatment with INC280 would be considered to have clinically relevant efficacy in a cohort/sub-cohort if an ORR of ~35% is observed in that cohort for the corresponding primary analysis.

In addition, 5 hypotheses will be tested as following for the cohorts/sub-cohorts respectively ( $H_{i0}$  and  $H_{i1}$  correspond to cohort/sub-cohort i where  $i=1a, 1b, 2, 3$  or  $4$ )

$H_{i0}$ : ORR  $\leq 25\%$

In favor of the alternative

$H_{i1}$ : ORR  $> 25\%$

For Sub-cohorts 5a, 5b and Cohort 7, treatment with INC280 would be considered to have clinically relevant efficacy if an ORR of ~55% is observed in that cohort for the corresponding primary analysis. In addition, 3 hypotheses will be tested as following for the cohorts/sub-cohorts ( $H_{i0}$  and  $H_{i1}$  correspond to Sub-cohort i where  $i=5a, 5b$  or  $7$ ):

$H_{i0}$ : ORR  $\leq 35\%$

In favor of the alternative

$H_{i1}$ : ORR  $> 35\%$

The tests will be performed based on the exact CI for ORR in each cohort/sub-cohort using a one-sided  $\alpha=0.025$  level. Based on historical data, as referred in [Section 1.1.1](#), a 25% ORR is a reasonable threshold to be considered as clinically relevant in this specific setting of second and third line advanced NSCLC patients ([de Marinis 2008](#), [Weiss 2013](#), [NCCN Guidelines 2014](#)) in Cohorts/Sub-cohorts 1a, 1b, 2, 3 and 4. Similarly, a 35% ORR is a reasonable threshold to be considered as clinically relevant in the treatment-naïve setting for advanced NSCLC patients ([Zhou 2015](#), [Scagliotti 2008](#)) in Sub-cohorts 5a, 5b and Cohort 7. Since a one sided  $\alpha=0.025$  is used for a particular hypothesis testing, the testing will be conducted based on two-sided 95% exact confidence interval. The null hypothesis will be rejected if the lower bound of the two-sided 95% exact CI is  $>25\%$  in Cohorts/Sub-cohorts 1a, 1b, 2, 3 and 4. And

the null hypothesis will be rejected in Sub-cohorts 5a and 5b if the lower bound of the two-sided 95% exact CI is >35%.

No hypothesis testing is planned for Cohort 6.

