- The updated analyses for **all MET mutant patients** (Cohorts 4, 5b and 6, and 7) will be conducted when Last Patient Last Visit is reached.
- Data from cohorts (Cohort 1-7) will be included for patient disposition, baseline characteristics and safety analyses. Patient disposition, baseline characteristics and safety analyses will also be presented combining the MET mutant patients (pre-treated, treatment-naïve and all MET mutant patients) and all amplified patients (complementary subgroup to MET mutant patients).
- Data from MET mutant cohorts (Cohort 4, 5b, 6 and 7) will be included for efficacy a [REDACTED] They will also presented combining the MET mutant patients (pre-treated and treatment-naïve MET mutant patients).
- No PK analyses will be included in this report as no additional PK samples are analyzed at this time.

[REDACTED]

All available data from all patients will be summarized in the final Clinical Study Report (CSR).

[Section 4.1](#) provides further details regarding data to be included in the analyses.

General presentation of descriptive summaries

Qualitative data (e.g., gender, race) will be summarized by frequency counts and percentages. Percentages will be calculated using the number of patients in the relevant population or subgroup as the denominator.

Continuous data (e.g., age, body weight) will be summarized by appropriate descriptive statistics (i.e. mean, standard deviation, median, minimum, and maximum).

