2.7.2 Statistical hypothesis, model, and method of analysis

The primary analysis will be performed on the FAS. The primary efficacy endpoint ORR will be estimated and the exact 95% confidence interval (CI) ([Clopper and Pearson 1934](#)) provided by cohort.

Treatment with INC280 will be considered to have clinically relevant efficacy in cohort (1-4) if an ORR of $\sim 35\%$ is observed in that cohort with lower bound of exact 95% CI greater than 25%. Whereas, in cohorts (5a and 5b and 7), treatment with INC280 will be considered to have clinically relevant efficacy if an ORR of $\sim 55\%$ is observed in that cohort with lower bound of exact 95% CI greater than 35%.

No hypothesis testing is planned for cohort 6.

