Table 2-10 Number of Responders for Various Number of Evaluable Patients at Interim Analyses by Required Probability of Success for Cohort 1a, Cohort 1b, Cohort 2 and Cohort 4

Number of Evaluable patients at IA	Responders at IA	Probability of Success
26	6	0.0368
26	7	0.1050
27	7	0.0765
27	8	0.1829
28	7	0.0543
28	8	0.1398

Number of Evaluable patients at IA	Responders at IA	Probability of Success
29	7	0.0377
29	8	0.1044
30	8	0.0760
30	9	0.1792
31	8	0.0540
31	9	0.1369
32	8	0.0373
32	9	0.1020
33	9	0.0740
33	10	0.1739
34	9	0.0523
34	10	0.1323
35	10	0.0980
35	11	0.2152

Cohort 3

With 20 evaluable patients for interim analysis in Cohort 3 if ≤ 5 responses (POS=0.0999) are observed then the cohort will be stopped for futility. All evaluable patients at the time of the data cut-off for the interim analysis will be used to obtain the futility boundary using the POS criteria. Further details of POS are provided in [Table 2-11](#). If at the time that the 20th patient is enrolled a minimum of 6 responders have not yet been observed, accrual in the cohort may be temporarily suspended until either the minimum number of 6 responders are observed or results of the interim analysis allow the cohort to continue.

Table 2-11 Probability of Success at the Final Analysis Based on Various Number of Responders Observed at IA for Cohort 3 (MET GCN less than 4)

Responder at IA out of 20 evaluable patients at IA	Probability of Success
1	0.0001
2	0.0009
3	0.0066
4	0.0309
5	0.0999
6	0.2379
7	0.4382
8	0.6533

3 Changes to protocol specified analyses

Not applicable.

4 Additional details on implementation of statistical methodology

The sections below contain additional details on statistical methodology that will be included in Appendix 16.1.9 (Documentation of Statistical Methods) of the CSR as well as rules details on programming rules that will be followed to implement the analyses described in [Section 2](#).

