4.6 Efficacy endpoints

For further details on efficacy endpoints, see Section 14 (Appendix II) of the protocol. For the evaluation of tumor-response related endpoints, response is assessed by investigator and BIRC according to RECIST 1.1.

Response and progression evaluation will be performed according to the Novartis RECIST 1.1 guidelines, included in Section 14 (Appendix II) of the CINC280A2201 protocol.

The text below gives more detailed instructions and rules needed for programming of the analyses described in [Sections 2.7](#) and [2.8.1](#).

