4.6.4 Confidence interval and p-value for response rate

ORR will be summarized in terms of percentage rates with 95% CIs. An exact binomial confidence interval (implemented using SAS procedure FREQ with EXACT statement for one-way tables) will be calculated ([Clopper & Pearson, 1934](#)).

SAS procedure FREQ will be used to estimate the proportion of responders (binary outcome = 1 or “Yes”), along with the associated 95% ($=100 \times (1 - \text{two-sided alpha level})$) two-sided Pearson-Clopper CI and exact one-sided p-value for the hypothesis test of the *null proportion* (0.25). These estimates are obtained as follows:

```
proc freq data = dataset;
  table binary event /
    binomial(
      p = null proportion
      level = "Yes")
    alpha = two-sided alpha level;
  exact binomial;
```

When there are no responders, SAS does not produce a CI by default. To obtain a CI in this situation, PROC FREQ is used as specified above except changing **level**="No". From the results of this modified procedure, the values in percent of the LCL and UCL of a 0% response rate are calculated as follows:

$$\text{LCL}_{\text{LEVEL}=\text{"Yes"}\ (\%)} = 100\% - \text{UCL}_{\text{LEVEL}=\text{"No"}\ (\%)}$$

$$\text{UCL}_{\text{LEVEL}=\text{"Yes"}\ (\%)} = 100\% - \text{LCL}_{\text{LEVEL}=\text{"No"}\ (\%)}$$

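### SAP 4.6.4 gives 0.25 as the only null for the exact ORR p-value, but the protocol null for treatment-naïve Cohorts 5b and 7 is 35%

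*SAP*

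**What the plan says.** **SAP 4.6.4**, on the confidence interval and p-value for response rate, asks for the two-sided Clopper-Pearson interval and an "exact one-sided p-value for the hypothesis test of the *null proportion* (0.25"; the parenthesis closes there. The SAS template that follows has a placeholder for the null, and 0.25 is the only number the section offers to fill it. SAP 4.6 introduces this material as binding on programming: "The text below gives more detailed instructions and rules needed for programming of the analyses described in" Sections 2.7 and 2.8.1.

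**Protocol 10.4.2** sets two nulls. For Cohorts 1a, 1b, 2, 3 and 4 it is ORR at most 25%. For 5a, 5b and 7 it is ORR at most 35%, with the rationale "Similarly, a 35% ORR is a reasonable threshold to be considered as clinically relevant in the" treatment-naïve setting. Each test is at one-sided 0.025, and "the testing will be conducted based on two-sided 95% exact confidence interval".

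**SAP 2.7.2** keeps both thresholds as confidence limits. For 5a, 5b and 7 an ORR of about 55% counts as clinically relevant if it "is observed in that cohort with lower bound of exact 95% CI greater than 35" per cent. It plans no hypothesis test for Cohort 6.

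**SAP 2.1** fixes the scope of this report: "Data from MET mutant cohorts (Cohort 4, 5b, 6 and 7) will be included for efficacy".

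**SAP Section 3**, headed "Changes to protocol specified analyses", is marked as not applicable.

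**The concern.** The programming rule conflicts with the protocol and with the SAP's own Section 2.7.2. It cannot be read as a deliberate change, since Section 3 declares none. Of the four cohorts in this report's efficacy analysis, 0.25 is the right null only for Cohort 4. It is wrong for 5b and 7, and Cohort 6 has no test.

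For any result with at least one responder, the upper-tail probability is smaller under 0.25 than under 0.35, so the error always runs in the favourable direction. The report could show a p-value below 0.025 for a treatment-naïve cohort whose confidence limit fails the 35% criterion. A reader would then have two results for the same primary endpoint pointing in different directions, with nothing to show that the p-value refers to another threshold.

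**Working it through.** **Inputs.** Planned n = 27 for each of 5a, 5b and 7 (protocol 10.8, SAP 2.9); nulls 0.25 (SAP 4.6.4) and 0.35 (protocol 10.4.2); one-sided level 0.025; success requires the exact 95% lower limit to exceed 35% (SAP 2.7.2).

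**Formulas.** One-sided p for r responders: P(X ≥ r), X ~ Binomial(n, p0). Clopper-Pearson lower limit: the 0.025 quantile of Beta(r, n − r + 1).

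**Step 1: reproduce the plan's figures.** 15/27 gives a lower limit of 35.3%, as in protocol Table 10-6 and SAP Table 2-5. P(X ≥ 15) at true ORRs of 40, 45, 50, 55, 60 and 65% is 7.43, 18.15, 35.06, 55.62, 74.99 and 88.94%. Protocol Table 10-9 and SAP Table 2-8 state 7.4, 18.1, 35.1, 55.6, 75.0 and 88.9%. The plan's own operating characteristics therefore rest on the 35% rule, met from 15 responders.

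**Step 2: the p-value under each null, n = 27.**

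| Responders | p, null 0.25 | p, null 0.35 | Exact lower 95% limit | Limit above 35%? |
|---|---|---|---|---|
| 12 | 0.0216 | 0.202 | 25.5% | no |
| 13 | 0.0078 | 0.111 | 28.7% | no |
| 14 | 0.00245 | 0.054 | 31.9% | no |
| 15 | 0.0007 | 0.0229 | 35.3% | yes |

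Under 0.35, p first falls to 0.025 or below at 15 responders, which is exactly the confidence-limit rule. Under 0.25 it does so at 12.

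**Step 3: how often this would show.** At a true ORR of 35%, P(X ≥ 12) = 0.2024 and P(X ≥ 15) = 0.0229. The chance of a p-value at or below 0.025 alongside a failed limit is the difference, 0.2024 − 0.0229 = 0.1795. The same probability, P(12 ≤ X ≤ 14), is:

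| True ORR | 35% | 45% | 50% | 55% | 72% |
|---|---|---|---|---|---|
| P(12 ≤ X ≤ 14) | 0.1795 | 0.4151 | 0.4284 | 0.346 | 0.020 |

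**Step 4: other cohort sizes.** SAP 2.2 gives N = 60 for 5b and 7 together, so they cannot both be 27 (2 × 27 = 54), and the split is not stated. Taking n from 25 to 35 as an assumed range, the p-value under 0.35 agrees with the confidence-limit rule at every n. The p-value under 0.25 crosses 0.025 three or four responders too early. Its false-positive rate at a true ORR of 35% runs from 12.5% (n = 25) to 23.6% (n = 33).

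**Step 5: the one treatment-naïve result in the documents.** Protocol 1.2.1.2.2 reports 72.0% in "patients (n=25, Sub-cohort 5b", that is 0.72 × 25 = 18 responders. The exact interval is 50.6% to 87.9%, matching the protocol. p is 0.000001 against 0.25 and 0.0002 against 0.35.

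**The case against.** The strongest reply is that little depends on this p-value. The protocol tests through the exact interval, and SAP 2.7.2 states the 35% limit correctly. That stands: the success decision, the ORR and the interval do not change.

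It can also be said that Section 2.7 names no p-value, that the SAS argument is only a placeholder, and that a careful programmer would find 35% elsewhere in the SAP. This stands in part. Whether a p-value reaches a table is an inference, but the heading and text of 4.6.4 both specify one. The sentence before the code gives the null as 0.25, and nothing there points to another value.

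On timing, SAP 2.1 lists the primary analyses of 5b (cut-off 15-Apr-2019) and Cohort 7 (cut-off 30-Aug-2021) as earlier reports, so this SAP governs an update. That lowers the stakes, but the update still reports ORR for both cohorts.

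On size, the 12 to 14 responder range belongs to n = 27 and shifts with the actual n. The chance of a mismatch is largest for true rates around 45% to 50% and is only 2.0% at 72%. Both points are fair, and the working shows them. Finally, a p-value against 25% and an interval compared with 35% do not contradict each other in logic. The harm is that the p-value would be read as the test of the protocol's hypothesis.

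**Conclusion.** The point holds. SAP 4.6.4 is wrong as written for Cohorts 5b and 7, and for 5a if the section were applied to it. It should be fixed, but it is confined to the reported p-value.

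At n = 27 the p-value is too small by a factor of 9.4 at 12 responders (0.20240/0.02162) and 34 at 15 (0.02292/0.00067). Read against 0.025, it has a 20.2% false-positive rate at the protocol null, compared with 2.3% for the correct test. These figures assume the planned n and that 4.6.4 is followed literally. The mismatch persists at every n checked from 25 to 35. For the 5b result quoted in the protocol the conclusion would not change. The documents give no Cohort 7 result, so the effect there cannot be judged.

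**What to change.** In SAP 4.6.4, state the null proportion by cohort: 0.25 for 1a, 1b, 2, 3 and 4, and 0.35 for 5a, 5b and 7. Add that no p-value is produced for Cohort 6, for which SAP 2.7.2 plans no test. The same is proposed for the pooled sets, for which that section sets no threshold.

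Alternatively, delete the p-value from 4.6.4 and report only the ORR with its exact interval, which is the protocol's test.

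The cost is one sentence in the SAP and one macro parameter that varies by cohort. Any p-values shown for 5b and 7 become larger, and no success decision changes.

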4.6.5 Baseline

Baseline is the result of an investigation describing the “true” uninfluenced state of the patient. The last available assessment before or on the start date of study drug is defined as “baseline” value or “baseline” assessment.

4.7 Safety evaluations

The text below gives more detailed instructions and rules needed for programming of the analyses described in [Section 2.8.2](#).

4.7.1 Multiple assessments within post-baseline visits

For all analyses regarding abnormal assessments or analyses based on worst or best post-baseline value (laboratory, ECGs, vital signs, ECOG performance status), all post-baseline values will be included (scheduled, unscheduled, repeat). All unscheduled and repeat measurements will be included in listings.

Laboratory Data

For laboratory data, assessments can be collected from both local and central laboratory on the same date. For shift tables using CTC grades to compare baseline to the worst post-baseline value, the assessment with worst post-baseline value is used for analyses irrespective of the source. For LFT summaries, where concurrent measurements are used in the calculation of number and percentage of patients with worst post-baseline values, the assessment with worst post-baseline value is used (since worst values are based on the largest ratio of lab value to its ULN for each patient) although the worst values for the different parameters may be coming from different laboratories.

ECGs

For all patients, 3 ECGs are targeted to be measured at the protocol-defined (nominal) time-points. If a patient has more than one measurement at a nominal scheduled time point, the average of all available measurements associated with the nominal time point will be used for the analyses. For unscheduled visits, measurements taken within 15 min interval will also be averaged and used for analysis.

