#### **6.3.4.1 Follow up on potential drug-induced liver injury cases**

Patients with transaminase increase combined with TBIL increase may be indicative of potential DILI, and should be considered as clinically important events.

The threshold for potential DILI may depend on the patient's baseline AST/ALT and TBIL values; patients meeting any of the following criteria will require further follow-up as outlined below:

- For patients with normal ALT and AST and TBIL value at baseline: AST or ALT  $> 3.0 \times$  ULN combined with TBIL  $> 2.0 \times$  ULN
- For patients with elevated AST or ALT or TBIL value at baseline: [AST or ALT  $> 2 \times$  baseline AND  $> 3.0 \times$  ULN] OR [AST or ALT  $> 8.0 \times$  ULN], whichever is lower, combined with [TBIL  $> 2 \times$  baseline AND  $> 2.0 \times$  ULN]

Medical review needs to ensure that liver test elevations are not caused by cholestasis, defined as: ALP elevation  $> 2.0 \times$  ULN with R value (ALT/ALP in  $\times$  ULN)  $< 2$  in patients without bone metastasis, or elevation of ALP liver fraction in patients with bone metastasis.

In the absence of cholestasis, these patients should be immediately discontinued from study drug treatment, and repeat LFT testing as soon as possible, preferably within 48 hours from the awareness of the abnormal results. The evaluation should include laboratory tests, detailed history, physical assessment and the possibility of liver metastasis or new liver lesions, obstructions/compressions, etc.

- Laboratory tests should include ALT, AST, albumin, creatine kinase, total bilirubin, direct and indirect bilirubin, GGT, prothrombin time (PT)/INR and alkaline phosphatase.
- A detailed history, including relevant information, such as review of ethanol, concomitant medications, herbal remedies, supplement consumption, history of any pre-existing liver conditions or risk factors, should be collected.
- Further testing for acute hepatitis A, B, C or E infection and liver imaging (eg, biliary tract) may be warranted.
- Obtain PK sample, as close as possible to last dose of study drug, if PK analysis is performed in the study.
- Additional testing for other hepatotropic viral infection (CMV, EBV or HSV), autoimmune hepatitis or liver biopsy may be considered as clinically indicated or after consultation with specialist/hepatologist.

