- Shift tables using CTC grades to compare baseline to the worst post-baseline value for laboratory parameters with CTC grades
- Shift tables using low, normal, high (as well as low and high combined) classifications to compare baseline to the worst post-baseline value for laboratory parameters where CTC grades are not defined.
- New or worsened abnormalities for laboratory parameters based on CTC grade
- Trends of renal function parameters (creatinine, BUN) over time (baseline and selected on-treatment time-points, See [Table 4-6](#)) will be displayed via boxplots based on time windows and corresponding tables displaying the statistics used for the box plots by the selected time points.

The following lab parameters will be summarized by cohort:

- Hematology: absolute lymphocytes, absolute neutrophils, hemoglobin (anemia), WBC, platelet counts, absolute basophils, absolute eosinophils, absolute monocytes, hematocrit
- Biochemistry: alkaline phosphatase (ALP), SGPT (ALT), SGOT (AST), total bilirubin, amylase, potassium, sodium, creatinine, glucose (hypo only), phosphate, albumin, calcium, magnesium, creatinine, direct bilirubin, blood urea nitrogen (BUN), GGT, lipase.
- For bi-directional parameters, both hyper and hypo summaries will be presented.

The following laboratory parameters will be presented in listings and will not be summarized:

- Urinalysis: macroscopic panel (dipstick) (bilirubin, blood, glucose, WBC, pH, protein, specific gravity), Urinalysis Microscopic panel (RBC, WBC, casts).
- Coagulation: INR, pro-thrombin time (PT) or Quick Test

The following listings will be produced for the laboratory data for all laboratory parameters where CTC grades are defined:

- Listing of patients with laboratory abnormalities of CTC grade 3 or 4
- Listing of all laboratory data with values flagged to show the corresponding CTC grades and the classifications relative to the laboratory reference ranges.

Liver function parameters of interest are total bilirubin (TBIL), ALT, AST and alkaline phosphatase (ALP). The number (%) of patients with worst post-baseline values will be summarized by cohort in the following categories:

- ALT >3×ULN, >5×ULN, >8×ULN, >10×ULN, >20×ULN
- AST >3×ULN, >5×ULN, >8×ULN, >10×ULN, >20×ULN
- ALT or AST >3×ULN, >5×ULN, >8×ULN, >10×ULN, >20×ULN
- TBIL > 2×ULN, >3×ULN

Combined and concurrent values post-baseline

- ALT or AST > 3×ULN & TBIL > 2×ULN
- ALT or AST > 3×ULN & TBIL > 2×ULN & ALP \geq 2×ULN

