- ALT or AST > 3×ULN & TBIL > 2×ULN & ALP < 2×ULN

Combined elevations values post-baseline (regardless of baseline levels)

- ALT or AST > 3×ULN & TBIL > 2×ULN
- ALT or AST > 3×ULN & TBIL > 2×ULN & ALP \geq 2×ULN
- ALT or AST > 3×ULN & TBIL > 2×ULN & ALP < 2×ULN

Combined elevations values post-baseline by baseline levels

AST/ALT \leq ULN at baseline

- ALT or AST > 3×ULN & TBIL > 2×ULN
- ALT or AST > 3×ULN & TBIL > 2×ULN & ALP \geq 2×ULN
- ALT or AST > 3×ULN & TBIL > 2×ULN & ALP < 2×ULN

AST/ALT > UNL at baseline

- Elevated ALT or AST & TBIL (>2×Baseline and 2×ULN)
- Elevated ALT or AST & TBIL (>2×Baseline and 2×ULN) & ALP \geq 2×ULN
- Elevated ALT or AST & TBIL (>2×Baseline and 2×ULN) & ALP < 2×ULN

with Elevated AST or ALT defined as: >3×ULN if \leq ULN at baseline, or (>3×Baseline or 8×ULN) if > ULN at baseline

In addition, a listing of all TBIL, ALT, AST and ALP values for patients with a post-baseline TBIL > 2×ULN, ALT > 3×ULN or AST > 3×ULN will be provided.

The relationship between post-baseline increases in ALT/AST and total bilirubin will be shown using eDISH plot: peak values of Total bilirubin vs peak values of ALT/AST at any time during the course of treatment (not necessarily concurrent).

Analysis of time to first occurrence of grade 3/4 AST/ALT (whichever occurs first) will be done. Time to first occurrence of grade 3/4 AST/ALT and duration of the first occurrence of grade 3/4 AST/ALT will be summarized using Kaplan-Meier method. Patients with grade 3/4 AST/ALT at baseline will be excluded from the analysis. Median together with 95% CI as well as 25th and 75th percentiles will be presented. In addition, the median time to occurrence for the subset of patients who experienced the event of interest will be calculated. Simple descriptive statistics

(median, min and max, 25th and 75th percentiles) will be presented. The probabilities at selected time points and the associate 95% CI will also be summarized.

Duration of first occurrence of grade 3/4 AST/ALT will be presented for the subset of patients who experienced the event. Median together with 95% CI as well as 25th and 75th percentiles will be presented.

ECGs

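### SAP 4.7.1 takes the largest ratio to ULN for ALP as for the other liver tests; this can only move patients out of the ALP <2×ULN rows, so that sub-row can be undercounted

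*SAP*

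**What the plan says.** SAP 2.8.2 names total bilirubin, ALT, AST and ALP as the liver parameters of interest. It introduces the tables with "The number (%) of patients with worst post-baseline values will be summarized by cohort in the following categories". ALT, AST and bilirubin have threshold rows of their own; ALP appears only as a qualifier in the combined rows.

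There are several combined blocks. One is headed "Combined and concurrent values post-baseline". The others count combined elevations without that label, first regardless of baseline and then by baseline ALT/AST. Each block has a parent row without ALP and two sub-rows that split it at ALP 2×ULN. The lower sub-row reads, for example, "ALT or AST > 3×ULN & TBIL > 2×ULN & ALP < 2×ULN".

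SAP 4.7.1 says how the values are chosen. All post-baseline values count, including unscheduled and repeat ones. For laboratory data it notes that "assessments can be collected from both local and central laboratory on the same date". For the liver summaries it uses the worst value, "although the worst values for the different parameters may be coming from different laboratories", because "worst values are based on the largest ratio of lab value to its ULN for each patient". No parameter is excepted. The SAP does not say what interval makes values concurrent.

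**The concern.** The sub-rows separate two patterns. In Protocol 6.3.4.1, "Medical review needs to ensure that liver test elevations are not caused by cholestasis", and ALP above 2×ULN is part of the definition of cholestasis. Raised transaminases and bilirubin without raised ALP are therefore the pattern of concern for drug-induced liver injury, and a higher ALP makes a case look less worrying. A rule that always takes the highest ALP is cautious for every liver test except the one used to make this split.

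Total ALP can also be high for reasons outside the liver. For patients with bone metastases the protocol looks at the ALP liver fraction instead of total ALP (6.3.4.1 and footnote c of Table 6-3). The SAP split uses total ALP only.

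Hepatotoxicity is an adverse event of special interest in both documents. Patients meeting the combined criteria are likely to be few, so one patient in the wrong sub-row could change how the table reads.

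**Working it through.** The documents give no count or rate for these rows, so there is no figure to reproduce. The check is one of direction, followed by illustrations.

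**Direction.** Let a₁, …, a_k be the ALP/ULN ratios eligible for one patient in the parent row.

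- Under the largest-ratio rule the patient is in the lower sub-row only if max(a₁, …, a_k) < 2.
- If the maximum is below 2, every aᵢ is below 2, including the ALP at the time of the liver event. The converse is false.
- So the patients in the lower sub-row under the maximum are a subset of those placed there by any single ALP value. Moves go only from <2 to ≥2. The parent row changes by 0, because ALP is not part of it.

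**Examples (assumed values, as multiples of ULN).**

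| Situation | ALT | TBIL | ALP values | ALP under the rule | Row under the rule | Row otherwise |
|---|---|---|---|---|---|---|
| Same day, two laboratories | 9.0 | 2.6 | central 1.7, local 2.1 | 2.1 | ≥2 | <2 (lower or central ALP) |
| Two dates, any-time block | 9.0 | 2.6 | 1.4 at the event, 2.3 at another visit | 2.3 | ≥2 | <2 (ALP at the event) |

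**Where each route can operate.**

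- *Concurrent block.* A patient moves only if same-day local and central ALP lie on either side of 2×ULN. Protocol 7.2.2.5 has local values entered only when the severity grade differs from the central one. Neither document gives grade limits for ALP, so they do not show whether a 1.7/2.1 pair would be recorded. This route is probably rare.
- *Any-time blocks.* Nothing ties the ALP to the date of the other elevations. Read with the rule that all post-baseline values count, a peak ALP from another on-treatment date, or from the 30 days after discontinuation that SAP 2.8.2 allows for laboratory summaries, can decide the row.

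**Illustrative size.** Relative loss from the lower sub-row = 1 − (share with maximum ALP <2) / (share with single ALP <2), simulated among parent-row patients with log-normal ALP.

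| Scenario | Assumptions | Share <2, single ALP → maximum | Relative loss |
|---|---|---|---|
| Same-day duplicate for every patient, low end | median 1.0, laboratory log-SD 0.05 | 0.9166 → 0.9080 | 0.9% |
| Same-day duplicate for every patient, high end | median 2.0, laboratory log-SD 0.15 | 0.5004 → 0.4353 | 13.0% |
| Peak over visits, low end | median 1.0, 3 visits, within-patient log-SD 0.15 | 0.948 → 0.914 | 3.6% |
| Peak over visits, high end | median 1.5, 10 visits, within-patient log-SD 0.30 | 0.717 → 0.346 | 51.8% |

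The between-patient log-SD was 0.5 in the duplicate scenarios and 0.4 in the peak scenarios. In 1,000,000 simulated pairs per duplicate scenario no patient moved from ≥2 to <2. The medians, SDs and visit numbers are assumptions, and the duplicate rows suppose a second laboratory value for everyone, which Protocol 7.2.2.5 makes unlikely.

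**The case against.** The strongest reply is that the 4.7.1 sentence is a source rule. Its paragraph opens with local and central results from one date, refers to concurrent measurements and does not name ALP. On that reading the SAP is merely silent on which ALP decides the any-time rows. This stands in part: the point needs 2.8.2 and 4.7.1 read together. But 2.8.2 puts ALP among the parameters and introduces the rows as worst values, and 4.7.1 gives the only definition of worst. A programmer following the text would take the highest ALP.

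The second reply is that nothing is hidden. The parent rows ignore ALP. SAP 2.8.2 also plans a listing of all four tests for every flagged patient, and an eDISH plot of ALT/AST against bilirubin. The protocol has cholestasis judged case by case, and confirmed cases without another cause reported as SAEs. All of this stands. It limits the consequence but does not correct the tabulated sub-row.

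Two stronger readings are tempting and are not supported:

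- *The hepatic signal is biased towards safety.* The one-way error holds for a given parent row. The any-time blocks also pair ALT/AST and bilirubin peaks from different dates, which can add patients to the parent row. Against a truly concurrent count, the net error can go either way. Nor does the SAP label any row as its Hy's Law signal.
- *An ALP rise months after the liver event reclassifies it.* Table 6-3 and Protocol 6.3.4.1 require discontinuation when the combined criteria are met without cholestasis, and the laboratory summaries stop 30 days later. For patients managed per protocol such a late value falls outside the table. Earlier peaks and those within the 30 days remain possible.

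**Conclusion.** The point holds in a limited form. As written, the SAP lets the highest ALP decide the split, and for a given parent row that can only take patients out of the ALP <2×ULN sub-row. The sub-row can be undercounted; the documents do not show that it will be. The effect is probably rare in the concurrent block and more likely in the any-time blocks. Its size in this trial cannot be computed: the ranges of about 1% to 13% and about 4% to 52% show only how far the result depends on assumed ALP behaviour.

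The conclusion rests on two readings: that ALP falls under the largest-ratio rule because nothing exempts it, and that the any-time blocks draw on all post-baseline values. It concerns a descriptive sub-row, but one for an adverse event of special interest, and the correction is cheap enough to be worth making.

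**What to change.** Make three changes to the SAP:

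1. In 4.7.1, limit the largest-ratio rule to ALT, AST and total bilirubin.
2. In the concurrent block, split by the ALP from the same assessment as the qualifying ALT/AST and bilirubin values. If two laboratories report ALP that day, use the lower ratio.
3. In 2.8.2, label the concurrent block as the one to read for potential Hy's Law, and footnote the any-time blocks to say that they use peak ALP. Peak ALP then remains there as a stated choice.

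The cost is a sentence or two of SAP text and minor programming. The ALP <2×ULN count may become slightly less favourable; the parent rows, the listing and the eDISH plot do not change.
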